4.2.3.3 Outcomes Research Analyses

Health status measured with EQ-5D-3L questionnaire

Health status is measured at baseline and Week 24 of the short-term double-blinded treatment period by the EQ-5D-3L questionnaire. The EQ-5D-3L is a generic, preference-based utility questionnaire and consists of two parts, the EQ visual analogue scale (VAS) and the EQ-5D-3L index (Kind 1996). The EQ VAS ranges from 0 = worst possible health to 100 = best possible health. The EQ-5D-3L index is a five-dimension questionnaire. The dimensions consist of mobility, self-care, usual activity, pain/discomfort and anxiety/depression. Each item has three levels: no problems, some problems and severe problems.

The change to from baseline to Week 24 LOCF in the EQ VAS and in EQ-5D-3L index will be analyzed separately, using ANCOVA models as outlined in Section 4.1.5.1. Point estimates and 2-sided 95% confidence intervals for the mean change within each treatment group, as well as the difference in mean change between each dapagliflozin treatment group and placebo, will be calculated. No p-values will be generated.

Proportions of subjects with assessments at baseline, Week 24 (LOCF), as well as a shift in the classification of the 5 dimensions of EQ-5D from baseline to Week 24 (LOCF), will be summarized.

All above mentioned analyses will use subjects in the primary efficacy dataset (i.e., Full Analysis Set) who have at least one baseline assessment and any post-baseline double-blind treatment period assessment.

Treatment Satisfaction measured with Diabetes Treatment Satisfaction Questionnaire status questionnaire

The DTSQ has been developed to assess patient's satisfaction with treatment and perception of change in hyper- and hypoglycaemia (Bradley 1994). The DTSQ status version (DTSQs) has 8 items. Each item has seven levels.

The change from baseline to Week 24 LOCF in overall DTSQs score and in individual item scores (which include scores for perceived frequency of hyperglycemia, for perceived frequency of hypoglycemia, for satisfaction with treatment, for convenience with treatment, for flexibility with treatment, for satisfaction with understanding of diabetes, for willingness to recommend treatment to someone else and for satisfaction to continue with current treatment) will be analyzed separately, using ANCOVA models as outlined in Section 4.1.5.1. Point estimates and 2-sided 95% confidence intervals for the mean change within each treatment group, as well as the difference in mean change between each dapagliflozin treatment group and placebo, will be calculated. No p-values will be generated.

All above mentioned analyses will use subjects in the primary efficacy dataset (i.e., Full Analysis Set) who have at least one baseline assessment and any post-baseline double-blind treatment period assessment.

Hypoglycemia Fear Survey II Worry Subscale

The HFS-II Worry Subscale is an 18-item questionnaire, in which responses are made on a 5-point Likert scale (where 0 = Never and 4 = Always). The HFS-II Worry Subscale has a score ranging from 0 to 72, with higher scores indicating increased fear of hypoglycemia.

The change from baseline to Week 24 LOCF in HFS-II score will be analyzed, using ANCOVA models as outlined in Section 4.1.5.1. Point estimates and 2-sided 95% confidence intervals for the mean change within each treatment group, as well as the difference in mean change between each dapagliflozin treatment group and placebo, will be calculated. No p-values will be generated.

All above mentioned analyses will use subjects in the primary efficacy dataset (i.e., Full Analysis Set) who have at least one baseline assessment and any post-baseline double-blind treatment period assessment.

4.2.4 Safety

This safety section describes safety analyses that will be conducted for the short-term double-blind treatment period.

The Treated Subjects data set will be used in all summaries of safety data in the short-term double-blind treatment period.

4.2.4.1 Adverse events

Adverse Events (AEs) will be classified by Primary System Organ Class (SOC) and Preferred Term (PT) according to the Medical Dictionary for Regulatory Activities (MedDRA). Summaries of AEs will use the version of MedDRA that is current at the time of database lock.

No statistical test will be performed to compare adverse event rates between treatment groups. This policy was adopted to recognize the lack of power and the potential for misleading

interpretation based on repeated statistical tests which increase the family wise Type I error level.

Counting rules for adverse events are described in Section 6.7.

In summaries by SOC and PT, AEs will be sorted by decreasing frequency within each SOC and PT according to the highest Dapagliflozin dose group. In summaries by PT, AEs will be sorted by decreasing frequency within PT according to the highest dapagliflozin dose group.

Separate pages to capture events of hypoglycemia are contained within the CRF.

Hypoglycemia or discontinuation due to hypoglycemia would not be reported on an AE CRF page unless the event fulfilled criteria for a Serious AE (SAE) in which case an SAE form would be completed. Hypoglycemia events that are reported as SAEs will be included in all summaries of AEs or SAEs (see Section All Adverse Events). Separate summaries will be provided including hypoglycemia events reported on that special CRF pages (see Section Hypoglycemia).

All Adverse Events

All adverse events (serious and non-serious, excluding hypoglycemic and DKA events that are not reported as SAEs) with onset during the short-term double-blind treatment period will be summarized by SOC, PT, and treatment group, for both the primary and sensitivity safety analyses. In addition, a subject listing of all reported adverse events will be produced, displaying all events (including pre-treatment events) that occurred prior to the start date of long-term treatment period. All adverse events (serious and non-serious) including all hypoglycemic events will also be summarized by treatment group.

AEs and SAEs with an onset from Day 1 of the short-term double-blind treatment period up to and including 4 days and 30 days respectively, after the last dose date in the short-term double-blind treatment period (or up to the start date of the long-term treatment period, whichever comes first) will be considered as occurring during the short-term double-blind treatment period.

In addition, number of subjects reporting any of the following during the double-blind treatment period will be summarized for all treated subjects:

- at least one adverse event
- at least one related adverse event
- deaths
- at least one SAE
- at least one related SAE
- SAE leading to discontinuation of study medication
- AE leading to discontinuation of study medication
- At least one SAE of hypoglycemia
- Hypoglycemia SAE leading to discontinuation of study medication

- At least one SAE of DKA
- DKA SAE leading to discontinuation of study medication

This summary will be repeated for Japanese subjects.

In addition, the following summaries will be provided for the short-term double-blind treatment period (excluding hypoglycemic events that are not reported as SAEs):

- Proportion of subjects with adverse events by SOC and PT in subgroups of subjects defined by age category (<35 years, ≥35 and <50 years, and ≥50 years), gender, and race.
- Most common adverse events by PT and treatment group (i.e., reported by ≥ 5% of subjects in any treatment group),
- Adverse events by SOC, PT, intensity and treatment group,
- Adverse events related to study medication by SOC, PT, and treatment group.

In addition to analyses of event incidence at the subject level, recurrence analyses will be performed at the event level. In order to prepare these summaries, the CRF data will be processed according to standard sponsor algorithms to categorize each line of patient data as a new occurrence or a continuation of an existing event. This determination will be based upon onset and resolution dates. Each line of patient data will represent the maximum severity observed as well as the last known assessed relationship to study medication by the investigator.

The following summary information will be provided:

- Total number and rate (exposure adjusted) of occurrences for all AEs occurring in at least 5% of the subjects treated. This data will be presented as the rate per 100 years of patient exposure. Exposure to study medication will be calculated according to approved standard sponsor algorithms as well. As an example, if 5 patients report 7 unique episodes of headache and had a combined cumulative exposure of 20 years to study medication, the incidence rate is reported as $7 / 20 * (100)$ or 35 cases per 100 patient years of exposure.

Additionally, a table will be provided displaying the unique instances of all AEs, i.e., after duplicates have been eliminated and overlapping and contiguous occurrences of the same event have been collapsed. No formal comparisons are made between treatments. No formal statistical testing will be performed, only summary statistics are provided.

For the purpose of clinical trial transparency, listing of most common non-serious AEs will be produced for posting at public websites (e.g., NIH's www.ClinialTrials.gov).

Deaths

All deaths recorded on the status page, the AE page, or SAE page (with a death date, cause of death, outcome or SAE categorization present) of the CRF will be considered a death in the analyses. Any deaths that occur during the study will be described in depth as narrative in the

CSR. A listing of all deaths that occur prior to the start date of long-term treatment period will be produced.

Serious Adverse Events

All SAEs (including hypoglycemic events) will be described in narratives, regardless of investigator assessment of causality. SAEs with an onset from Day 1 of the short-term double-blind treatment period up to and including 30 days after the last dose date in the short-term double-blind treatment period (or up to the start date of the long-term treatment period, whichever comes first) will be considered as occurring during the short-term double-blind treatment period.

SAEs occurring during the short-term double-blind treatment period will be summarized by SOC, PT, and treatment group for both the primary and sensitivity safety analyses. In addition, the proportion of subjects with related SAEs will be presented by SOC, PT, and treatment group. A listing of all SAEs will be produced, displaying all SAEs (including pre-treatment events) that occurred prior to the start date of long-term treatment period.

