4.2.4.2 Adverse events leading to discontinuation of study medication

AEs with an onset during the short-term double-blind treatment period reported with an action taken of discontinuation of study medication will be summarized by SOC, PT, and treatment group for both the primary and sensitivity safety analyses. This summary will include hypoglycemia and DKA events that are reported as SAEs. When summarizing AEs leading to discontinuation, no upper cutoff day windows (i.e. 4 days and 30 days from last dosing date in the short-term double-blind treatment period for AEs and SAEs respectively) are applied. For short-term double-blind period analyses, the only upper cutoff date is the last date of the short-term double-blind treatment period.

In addition, a subject listing of discontinuation due to AEs will be provided, displaying all events that led to discontinuation with an onset date prior to and including the last date of short-term double-blind treatment period, if any.

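### The adverse event summaries in SAP 4.2.4.1 use different rules for DKA not reported as an SAE, so subset tables can hold events that the parent table leaves out

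*SAP*

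**What the plan says.** Under All Adverse Events, SAP section 4.2.4.1 describes several overlapping summaries for the short-term period.

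- The main table by SOC, PT and treatment group covers serious and non-serious events, "excluding hypoglycemic and DKA events that are not reported as SAEs".
- A supplementary summary follows: "All adverse events (serious and non-serious) including all hypoglycemic events will also be summarized by treatment group". DKA is not mentioned.
- An overview table says that the "number of subjects reporting any of the following during the double-blind treatment period will be summarized for all treated subjects". Its lines include subjects with any event and with any related event, and no exclusion is stated for either. Serious DKA has its own line, "At least one SAE of DKA".
- Four further tables (age, gender and race subgroups; events in 5% or more of a group; intensity; related events) are produced "excluding hypoglycemic events that are not reported as SAEs". DKA is not named.

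For hypoglycemia the SAP explains the exclusion: "Separate pages to capture events of hypoglycemia are contained within the CRF", and such an event goes on an AE page only if it is serious. It says nothing comparable about DKA. Section 4.2.4.2, on events leading to discontinuation, pairs the two again: "This summary will include hypoglycemia and DKA events that are reported as SAEs".

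**The concern.** A table of related events, or of events by intensity, should be a breakdown of the table of all events. Here the parent table removes two kinds of non-serious event and the breakdowns remove one. Programmed literally, a DKA row could appear in the related-event table with no counterpart, or a smaller count, in the table of all events.

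DKA is named in the safety objectives (section 1.1), so its place in the general AE tables should be clear. At stake is whether those tables agree with one another, and whether at least one all-event summary can be relied on to contain every DKA. No hypothesis test or efficacy result is involved.

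**Working it through.** The plan gives no figure to reproduce, so the check is a comparison of the stated rules.

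| Summary (SAP section) | Non-serious hypoglycemia | Non-serious DKA |
|---|---|---|
| All events by SOC/PT (4.2.4.1) | excluded | excluded |
| Supplementary all-event summary (4.2.4.1) | included | not mentioned |
| Overview counts, any event and any related event (4.2.4.1) | no rule stated | no rule stated |
| Subgroup, most-common, intensity, related (4.2.4.1) | excluded | not excluded |
| Events leading to discontinuation (4.2.4.2) | only SAE-reported events named as included | only SAE-reported events named as included |

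The consequence depends on where non-serious DKA is recorded, which the SAP does not say.

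**Case A: it is in the AE data.** The parent table removes it and the four breakdown tables keep it, so the breakdowns need not nest in the parent. The overview line for any event, read literally, includes it and can exceed the total of the parent table.

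**Case B: it is captured outside the AE data, as non-serious hypoglycemia is.** The two exclusions then select the same AE records, and the parent and breakdown tables agree. But the supplementary summary says that it brings back hypoglycemia only, so no all-event summary is stated to contain all DKA. The SAP also leaves the separate capture of DKA undescribed.

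Either way the text needs a correction.

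**Scale.** Section 1.3 plans 256 subjects per arm.

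- One subject whose only event is a non-serious DKA: 1/256 = 0.0039, or 0.39 percentage points of any-AE incidence in the parent table.
- Threshold for the most-common table: 0.05 × 256 = 12.8, so 13 subjects in an arm.
- The SAP gives no DKA rate. If 4% of an arm had any DKA (an assumption), that is 0.04 × 256 = 10.2, about 10 subjects and fewer than 13. At that rate DKA would not enter the most-common table, and the mismatch would show only in the intensity, related and subgroup tables.

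**The case against.** The strongest reply is that nothing may differ in practice. Sections 4.2.4.1 and 4.2.4.2 both pair DKA with hypoglycemia, which suggests that the two are collected alike. If so, non-serious DKA never reaches the AE data and the shorter exclusion selects the same records as the longer one. This is a fair reading and it cannot be ruled out. It does not clear the text, because the supplementary summary would then restore one of the two event types and leave out the other.

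A second reply is that DKA is well covered elsewhere. Section 4.2.4.4 plans blinded adjudication, proportions, recurrence, rates by monthly interval, time to first event and a listing of adjudicated cases. Apart from the summary of discontinuations, none of these is limited to serious events. This stands, and it means that no DKA signal is hidden. However, that section plans no DKA summary by intensity or by relationship to study medication. Those breakdowns come only from the 4.2.4.1 tables whose rule departs from the parent.

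A reader might go further and infer that the headline AE incidence omits DKA. The SAP does not support this. Only DKA not reported as an SAE is removed, and only the SOC/PT table says so. Serious DKA stays in that table, and the overview line for any event states no DKA exclusion. Nor does the SAP support a claim that a particular number of subjects, or a particular arm, is affected.

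**Conclusion.** The inconsistency is real: within section 4.2.4.1, one rule removes non-serious DKA, another does not, and two summaries are silent on it. As written, the breakdown tables need not fit inside the table of all events. If DKA is collected separately, no all-event summary is stated to include all of it.

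The size is unknown. It is zero if every DKA is reported as an SAE. In Case B the parent and breakdown tables do not differ, and only the gap in the supplementary summary remains. Otherwise each affected subject with no other event is worth 0.39 percentage points in the SOC/PT table, assuming the planned 256 per arm. The tables are descriptive and untested, and the dedicated DKA analyses are unchanged. It is worth correcting because it concerns a named safety objective and the correction is small.

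**What to change.** State in section 4.2.4.1 on which CRF page non-serious DKA is recorded. Then apply one DKA rule to every summary in that section, including the overview counts and the supplementary all-event summary.

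- **If it is recorded on the AE page:** remove DKA from the exclusion for the SOC/PT table, so that it is counted throughout and only non-serious hypoglycemia is set aside.
- **If it is recorded elsewhere:** add DKA to the exclusion for the subgroup, most-common, intensity and related-event tables, and have the supplementary summary include all hypoglycemic and all DKA events.

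The SAP alone does not settle which branch applies. The DKA summaries in section 4.2.4.4 can stay as they are. The cost is a few words and one table-selection flag, with no new data. The reported AE incidence may rise slightly.

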1.2 Study design

[figure not shown]
This trial is a randomized, double-blinded, three-arm, parallel-group, placebo-controlled, multicenter trial to evaluate the efficacy and safety of dapagliflozin, when added to ongoing insulin therapy, in subjects with T1DM and inadequate glycemic control.

Potential subjects will be assessed for eligibility criteria at the screening visit. Eligible subjects will enter an 8-week lead-in period in order to optimize their diabetes management based on individual subject challenge to glycemic control (including hyperglycemia, hypoglycemia, erratic meal/exercise patterns, as defined by the investigator) and to assess the variability in blood glucose profiles and frequency of hypoglycemic episodes at baseline. No placebo or study medication will be provided during the lead-in period. On the Day 1 visit, subjects who meet all the protocol-specific enrollment and randomization criteria will be randomized into one of the three blinded treatment arms (dapagliflozin 5 mg QD, dapagliflozin 10 mg QD, or placebo QD) in a 1:1:1 ratio. Randomization will be stratified by the following factors to ensure equal representation across all treatment groups: 1) current use of CGM (this refers to an unblinded/personal device which may already be in use before using the blinded device as part of the study) categorized as yes vs. no; 2) method of insulin administration at baseline (multiple daily injections (MDI) three or more injections per day vs. continuous subcutaneous insulin infusion - CSII); and 3) baseline A1C $\geq 7.5\%$ and $< 9.0\%$ vs. $\geq 9.0\%$ and $\leq 10.5\%$.

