1.3 Number of subjects

The primary endpoint is the change from baseline in HbA1c to Week 24 visit.

With 243 subjects per treatment group with both baseline and at least one post baseline measurement, there is approximately 90% power to detect a difference in means of 0.35% between each dapagliflozin treatment group and placebo at the two-sided 0.0262 significance level (based on Dunnett and Tamhane step-up procedure) (Dunnett and Tamhane 1992), assuming a standard deviation (SD) of 1.1%. Assuming that 5% of subjects do not have a post-baseline assessment, a total of 768 subjects (256 subjects per treatment arm) need to be randomized to each dapagliflozin or placebo group in 1:1:1 ratio. Due to regulatory requirements, approximately 160 subjects from Japan will be included (of the total population of 768 subjects).

A mean reduction in the primary endpoint of change from baseline in HbA1c of 0.35% was used to determine sample size as this represents a clinically meaningful improvement in glycemic control under the current study design with adjustable background insulin dose. A lesser degree of reduction in HbA1c in combination with other beneficial outcomes in secondary endpoints may also be clinically important.

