2.1.5 Treated subjects dataset

The treated subjects dataset, aka, safety analysis set, consists of all subjects who received at least one dose of double-blind study medication during the short-term double-blind treatment period. The treated subjects dataset would include any subject who accidentally received double-blind study medication but was not randomized in the study. These subjects will be included in treated subject dataset analyses based on the treatment they received. For randomized subjects, all analyses using the treated subject dataset will be presented by randomized treatment group, except in cases where information was available which indicated

that a subject received a different treatment for the entire course of their participation in the study (or study period). In this case, the safety data for those subjects will be presented by the treatment actually received. In the case where a subject never received the treatment as assigned by randomization, then the safety data for that subject will be presented by the first treatment received.

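### The exposure-adjusted AE rate table has a 5% cut-off that reads as pooled over arms, while the common-AE table uses 5% in any arm, so some mid-frequency AEs seen mainly on dapagliflozin can drop out of the rate table

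*SAP*

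**What the plan says.** SAP section 4.2.4.1, under All Adverse Events, sets two row-selection rules close together.

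- Subject-level table: "Most common adverse events by PT and treatment group (i.e., reported by ≥ 5% of subjects in any treatment group".
- Event-level table, which counts recurrences and divides by patient exposure: "Total number and rate (exposure adjusted) of occurrences for all AEs occurring in at least 5% of the subjects treated". No treatment-group qualifier is attached.

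The denominator comes from two other places. Section 4.2.4 states: "The Treated Subjects data set will be used in all summaries of safety data in the short-term double-blind treatment period". Section 2.1.5 says this set "consists of all subjects who received at least one dose of double-blind study medication during the short-term double-blind treatment period", with no split by arm. No reason is given for the different cut-offs.

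Two further provisions bear on the point. The paragraph after the rate table adds a table of unique AE instances with no frequency threshold, but mentions no rate. Section 6.7.2 promises an exposure-adjusted summary at event level, but neither repeats nor changes the cut-off.

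**The concern.** The first rule names the treatment group and the second does not, so the natural reading is that the second is pooled over the three arms. A pooled cut-off is hardest to meet for an AE that occurs mainly on active treatment, because the placebo subjects add to the denominator and little to the numerator. The same AE can then be listed as common in one table and have no row in the other.

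What is at stake is the display of recurrence rates. The SOC/PT and common-AE tables count a subject once per term (section 6.7.1), so they do not show repeated episodes. Among the AEs of special interest in section 4.2.4.4, exposure-adjusted event rates are specified only for DKA and hypoglycemia. Genital and urinary-tract infections get recurrence categories and Kaplan-Meier curves. Volume depletion, renal events, fractures and hypersensitivity get numbers and percentages of subjects. For other terms, the thresholded table is the only one for which the plan clearly specifies a per-term event rate.

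**Working it through.** **Inputs.** Section 1.2: "dapagliflozin 5 mg QD, dapagliflozin 10 mg QD, or placebo QD) in a 1:1:1 ratio". Section 1.3: "a total of 768 subjects (256 subjects per treatment arm) need to be randomized". The document gives no AE frequencies, so those below are assumptions. I also assume that all 768 randomized subjects are dosed, 256 per arm.

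**The plan's own figures.** Section 1.3 claims "approximately 90% power to detect a difference in means of 0.35% between each dapagliflozin treatment group and placebo at the two-sided 0.0262 significance level" with SD 1.1% and 243 evaluable subjects per arm. Recomputed power for two means is 0.9004, and the required size at 90% is 243. Then 243 / 0.95 = 255.8, rounded up to 256, and 3 × 256 = 768. The worked rate example also reproduces: 7 / 20 × 100 = 35 per 100 patient-years.

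**Thresholds in subjects.**
- Any-arm rule: 0.05 × 256 = 12.8, so 13 subjects in one arm (13/256 = 5.08%).
- Pooled rule: 0.05 × 768 = 38.4, so 39 subjects (39/768 = 5.08%; 38/768 = 4.95% fails).

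**Rates needed under the pooled rule.** At 1:1:1 the pooled share is (p5 + p10 + pP)/3, so entry requires p5 + p10 + pP ≥ 15%.
- Both doses equal, placebo at q: (15% − q)/2 in each. This is 7.5% at q = 0, 7.0% at 1% and 6.5% at 2%. In whole subjects with none on placebo it is 39/512 = 7.6%, as an average of the two arms.
- One dose only, the other dose and placebo both at q: 15% − 2q. This is 15% at q = 0, 13% at 1% and 11% at 2%. In whole subjects at q = 0 it is 39/256 = 15.2%.

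**Illustrative counts (256 per arm).**

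| 5 mg / 10 mg / placebo | Total | Pooled | Highest arm | Common-AE table | Rate table, pooled |
|---|---|---|---|---|---|
| 15 / 15 / 3 | 33 | 4.30% | 5.9% | in | out |
| 18 / 18 / 0 | 36 | 4.69% | 7.0% | in | out |
| 19 / 19 / 0 | 38 | 4.95% | 7.4% | in | out |
| 18 / 18 / 3 | 39 | 5.08% | 7.0% | in | in |
| 20 / 20 / 3 | 43 | 5.60% | 7.8% | in | in |
| 5 / 20 / 5 | 30 | 3.91% | 7.8% | in | out |
| 0 / 38 / 0 | 38 | 4.95% | 14.8% | in | out |
| 13 / 13 / 13 | 39 | 5.08% | 5.1% | in | in |

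The last row is a background AE with no arm difference. It enters, while 19 / 19 / 0 does not.

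**Chance of a split listing.** Binomial simulation (200,000 draws, 256 per arm) gives the probability that an AE is in the common-AE table but not in the rate table, for assumed true rates on 5 mg / 10 mg / placebo: 77% at 6/6/1%, 51% at 7/7/1%, 68% at 3/9/2% and 12% at 8/8/2%.

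**The case against.** **The pooled reading is an inference.** The rate-table rule is not labelled overall or pooled. Elsewhere the SAP often says so when arms are combined (sections 4.1.3, 4.1.4, 4.2.1.2 and 4.2.1.3), and the wording could be shorthand for the any-arm rule just above it. This stands as a caution. Still, beside an explicit any-arm rule and with a treated set defined across arms, pooled is the plain reading. If it is not what was meant, the wording still allows two different tables to be programmed.

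**Different cut-offs are not a contradiction.** One governs a subject-level table and the other an event-level table, and both can be produced as written. That is true. The case for change is that the difference is unexplained and works against AEs concentrated on active treatment.

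**Most of the content appears elsewhere.** All AEs are tabulated by SOC, PT and arm without a threshold, unique instances are tabulated without a threshold, and section 4.2.2.1 gives patient-years by arm, so a reader with event counts by arm could form an approximate rate. Section 6.7.2 might be taken to cover the rates, but it states no cut-off. This largely limits the harm, though none of it clearly restores the per-term rate.

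A reader might also infer that the pooled rule removes the AEs with the largest arm differences. It does not. An AE at 8%/8%/0% is (8 + 8 + 0)/3 = 5.3% pooled and stays, while 7%/7%/0%, with a smaller difference, is 4.7% and goes. Nor is 7.6% a minimum in each active arm: 20 and 19 subjects suffice, as do 25 and 14 (9.8% and 5.5%).

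**Conclusion.** The two cut-offs differ and, read plainly, the rate table can leave out AEs that are common on dapagliflozin and rare on placebo. The loss is confined to a band. With none on placebo it runs from about 5% to 7.5% in both active arms, or from about 5% to 15% in one dose only. In the one-dose case half of the dilution comes from the other dapagliflozin arm, so placebo is not the sole cause. Any placebo events narrow the band, and more frequent AEs enter under either rule.

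This is a minor reporting inconsistency. The SAP plans no testing of AEs, so no estimate, test or decision rule changes. It would be too strong to conclude that safety findings are hidden: dropped terms remain in the SOC/PT, common-AE and unique-instances tables, and the AEs of special interest have their own summaries. The conclusion rests on the pooled reading and on about 256 treated subjects per arm. The AE frequencies are illustrative.

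**What to change.** In section 4.2.4.1, change the cut-off of the exposure-adjusted rate table to at least 5% of subjects in any treatment group, matching the common-AE table. An AE would then enter with 13 subjects in one arm instead of 39 overall. The change takes a few words and adds some rows to one table. It should be made before unblinding.
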